13.2 Data Management

Data management will be performed by [REDACTED]. Data collected during the trial will be recorded in the patient's eCRF by the investigational site staff.

13.3 Trial Monitoring

Sponsor or sponsor assigned monitors will conduct regular site visits to the investigational facilities for the purpose of monitoring various aspects of the trial. The investigator must agree to sponsor-authorized personnel having direct access to the clinical (or associated) files and clinical trial supplies (dispensing and storage areas) for all trial patients considered for trial entry for the purpose of verifying entries made in the eCRF, and assist with their activities, if requested. Adequate time and space for monitoring visits should be made available by the investigator.

The site must complete the electronic eCRFs in a timely manner and on an ongoing basis to allow regular review by the trial monitor. Further instruction will be provided in the eCRF Completion Guidelines.

The monitor will discuss the conduct and progress of the trial with the investigator and other site staff. The investigator must cooperate with the monitor to ensure that corrective action is

taken to resolve any problems noted in the course of the monitoring, and that the preventive measures are put into place to prevent recurrence of issues. In cases where compliance is not achieved, shipment(s) of the trial drug to the investigator will be discontinued and trial participation by that investigator will be terminated.

13.4 Inspections and Auditing Procedures

Before, during and after the trial, the sponsor or its representative may conduct audits at the investigative sites including, but not limited to, drug supply, presence of required documents, the informed consent process, and comparison of eCRFs with source documents. All medical records (progress notes) must be available for audit. The investigator agrees to participate in audits conducted at a convenient time in a reasonable manner.

Government regulatory authorities may also inspect the investigator. The investigator or designee should contact the sponsor/ [REDACTED] immediately if this occurs. He/she must cooperate fully with regulatory authorities or other audits conducted at a convenient time in a reasonable manner. The investigator will forward to the sponsor a copy of any inspection records received.

14. TRIAL MANAGEMENT AND MATERIALS

14.1 Data Collection

All data entered in the eCRF should be documented at the site. During each trial visit, a physician participating in the trial will maintain progress notes in the patient's medical records to document all significant observations. At a minimum, these notes will contain:

- That the patient has consented and is found eligible for the trial (as applicable).
- The date of the visit and the corresponding day or visit in the trial schedule (e.g., screening, Day 1, Day 15, etc.).
- General condition and status remarks by the patient, including any significant medical findings. The severity, frequency, duration and resolution of any reported AE, and the investigator's assessment as to whether or not the reported AE is trial drug-related.
- Changes in concomitant medications or dosages.
- A general reference to the procedures completed.
- The signature or initials of all physicians making an entry in the medical record (progress notes).

In addition, any contact with the patient via telephone or other means that provides significant clinical information will also be documented in the medical record (progress notes), as described above.

Information from the medical records (progress notes) and other source documents will be promptly transcribed to the appropriate section of the eCRF.

Changes to information in the medical record (progress notes), and other source documents will be initialed and dated on the day the change is made by the investigator or designee. If the reason for the change is not apparent, a brief explanation for the change will be written adjacent to the change.

Details on data validation, data transfers, origin and destination on the data, access to the transferred data, timing of the transfer and any actions that may be triggered by real-time review of those data will be documented in the data management plan.

14.2 Source Documents Maintenance

Source documents contain the results of original observations and activities of a clinical investigation. Source documents include, but are not limited to, medical records (progress notes), clinical and office charts, laboratory notes, pharmacy dispensing records, recorded data from automated instruments, photographic negatives, microfilm or magnetic media, x-rays, computer printouts, patient files and records kept at the pharmacy, laboratories and medico-technical departments involved in the clinical trial. There should only be one source defined at any time for any data element.

All source documents from this trial will be maintained by the investigator and made available for inspection by authorized persons. The original signed informed consent for each

patient shall be filed with records kept by the investigator and a copy shall be given to the patient.

14.3 Record Maintenance

All data derived from the trial will remain the property of Genmab A/S.

Records must be retained in accordance with the ICH Guidelines on GCP (R2). All essential trial documents including records of patients, source documents, eCRFs and trial drug inventory must be kept on file.

USA FDA regulations (21 CFR 312.62[c]) require that records and documents pertaining to the conduct of this trial and the distribution of investigational drug, including eCRFs, consent forms, laboratory test results and medical inventory records, must be retained by the Principal Investigator for two years after marketing application approval. If no application is filed, these records must be kept two years after the investigation is discontinued and the USA FDA and the applicable national and local health authorities are notified. The sponsor or their representative will notify the Principal Investigator of these events.

The investigator will not dispose of any records relevant to this trial without written permission from the sponsor, and will provide the sponsor the opportunity to collect such records. The investigator shall take responsibility for maintaining adequate and accurate hard copy source documents of all observations and data generated during this trial. Such documentation is subject to inspection by the sponsor, its representatives and regulatory authorities.

If an investigator moves, withdraws from an investigation or retires, the responsibility for maintaining the records may be transferred to another person who will accept responsibility. Notice of transfer must be made to and agreed by the sponsor.

14.4 Confidentiality

All information obtained during the conduct of the trial with respect to the patient's state of health will be regarded as confidential. For disclosure of any such information, an agreement will be obtained in writing.

The investigator must ensure that each patient's anonymity is maintained. On eCRFs and other documents submitted to the sponsor or the CRO, patients must not be identified. Instead, patients will only be known by the unique patient number allocated to them in order to ensure confidentiality on all trial documentation. Patients will retain this unique number throughout the trial. The investigator will keep a separate log of these codes.

In order to comply with government regulatory guidelines and to ensure patient safety, it may be necessary for the sponsor and its representative, ██████ personnel, the local research review board, or the USA FDA to review patients' medical records as they relate to this trial. Only the patient's unique number on the eCRFs will identify him/her, but their full names may be made known to a drug regulatory authority or other authorized government or health care officials, if necessary, and to personnel designated by the sponsor.

Documents that are not for submission to the sponsor (e.g., consent forms) will be maintained by the investigator in strict confidence, except to the extent necessary to allow

monitoring by the sponsor and designee, and auditing by regulatory authorities. No documents identifying patients will leave the investigative site and patient identity will remain confidential in all publications related to the trial.

15. ADMINISTRATION PROCEDURES

15.1 Regulatory Approval

Genmab A/S or their appointed agents will be responsible for ensuring that appropriate regulatory authority approvals are obtained, according to local country requirements.

No patient may enter the trial until this approval has been obtained. A copy of the approval (where one is provided, according to local country requirements) will be provided to the investigator and to the IEC(s)/IRB(s).

15.2 Protocol Amendments

In accordance with ICH Topic E6(R2) Guideline for GCP, the investigator should not implement any deviation from, or changes of the protocol without agreement by the sponsor and documented approval from the IEC/IRB of a protocol amendment, except where necessary to eliminate an immediate hazard(s) to trial patients, or when the change(s) involves only logistical or administrative aspects of the trial (e.g., change in monitor(s), change of telephone number(s)).

Any change to the protocol must be handled as a protocol amendment. Any potential amendment must be approved by the sponsor. A written amendment must be submitted to the appropriate regulatory authorities and to the IEC/IRB assuming this responsibility. The investigator must await IEC/IRB approval of protocol amendments before implementing the changes, except where necessary to eliminate apparent immediate hazard to patients. In these cases, the IEC/IRB must be notified within five days of the change.

All amendments to the protocol must be approved in writing by both the appropriate regulatory authorities and the IEC/IRB, except for administrative amendments, which require notification but not written approval. Once approved, the protocol amendment will be distributed to all recipients of the original protocol, with instructions to append the amendment to the protocol.

If, in the judgment of the local IEC/IRB, the investigator and/or sponsor, the protocol amendment alters the trial design, procedures and/or increases the potential risk to the patient, the currently approved written ICF will require modification. The modified ICF must also be reviewed and approved by the sponsor, appropriate regulatory authorities, and the IEC/IRB. In such cases, repeat informed consent must be obtained from patients enrolled in the trial before participation continues.

15.3 Protocol Adherence and Deviations

The protocol must be read thoroughly and the instructions must be followed. However, exceptions will be made in emergency situations when the protection, safety and well-being of the patient requires immediate intervention based on the judgment of the investigator or a responsible, appropriately trained and credentialed professional(s) designated by the investigator as a sub-investigator.

In the event of a significant protocol deviation due to an emergency, accident or error, the investigator or designee must contact the Medical Monitor at the earliest possible time by

telephone. This allows for an early joint decision to be made as to whether or not the patient should continue in the trial. The investigator, the sponsor and the Medical Monitor will document this decision.

15.4 Publication Policy

The sponsor acknowledges the investigator's right to publish the entire results of the trial, regardless of the outcome, in accordance with the Uniform Requirements for Manuscripts Submitted to Biomedical Journals of the International Committee of Medical Journal Editors (<http://www.icmje.org/icmje-recommendations.pdf>, updated December 2014).

The international Coordinating Investigator will, together with the sponsor, decide on the publication strategy and has the right to publish and present the results and methods as first author of multicenter publications. Co-authorship will be decided by the sponsor and the international Coordinating Investigator and will be limited to a number of persons who have contributed substantially in the design, analysis and conduct of the trial or the writing and presentation of results. The sponsor will have representation in the list of authors.

Publications are subject to the following conditions:

- No publication before the completion of the trial at all participating sites without written agreement with the sponsor.
- All proposed publications and presentations, including any modifications or amendments, shall be submitted to the sponsor for its review at least 30 days before such presentation or publication is submitted to any third party.
- Publications shall not disclose any sponsor confidential information and property (not including the trial results, which can be published as described elsewhere in this section).

15.5 Contractual and Financial Details

The investigator (and/or, as appropriate, the hospital administrative representative) and the sponsor will sign a clinical trial agreement prior to the start of the trial, outlining overall sponsor and investigator responsibilities in relation to the trial. The contract should describe whether costs for pharmacy, laboratory and other protocol-required services are being paid directly or indirectly. Financial Disclosure Statements will need to be completed, as requested by FDA CFR 21 part 54.

15.6 Insurance, Indemnity and Compensation

Genmab A/S undertakes to maintain an appropriate clinical trial insurance policy.

Deviations from the trial protocol - especially the prescription of a dose other than that scheduled in the trial protocol, other modes of administration, other indications and longer treatment periods - are not permitted and shall not be covered by the statutory patient insurance scheme.

15.7 Termination of the Trial

This trial may be terminated by the sponsor. The trial may also be terminated prematurely at any time when agreed to by both the investigators and the sponsor as being in the best interests of patients, and justified on either medical or ethical grounds. In terminating the trial, Genmab A/S, [REDACTED] and the investigator will ensure that adequate consideration is given to the protection of the patients' interests.

15.8 Investigator Trial File Management

The investigator is responsible for assuring that the Investigator Trial File is maintained. The Investigator Trial File will contain, but will not be limited to, the information listed below:

- (1) Investigator's Brochure;
- (2) Current signed version of the protocol and any previous versions of the protocol;
- (3) Protocol amendments (if applicable);
- (4) Operations Manual (if applicable);
- (5) Current ICF (blank) and any previous versions of the ICF;
- (6) Curricula Vitae of investigator(s) and sub-investigator(s) and a photocopy of their respective license(s) where required by law; original USA FDA Form 1572 (for all studies conducted under USA Investigational New Drug [IND] regulations), signed by all Principal investigators. The names of any sub-investigators must appear on this form. Investigators must also complete all regulatory documentation as required the ICH GCP and by local or national regulations;
- (7) Documentation of CA/IEC/IRB approval of the protocol, the ICF, any protocol amendments, and any ICF revisions;
- (8) All correspondence between the investigator, IEC/IRB, and the sponsor/designee relating to trial conduct;
- (9) Laboratory certification(s);
- (10) Patient management logs (screening log, etc.);
- (11) Monitoring log;
- (12) Trial drug invoices;
- (13) Delegation log;
- (14) Source document location list.

17. APPENDICES

17.1 Appendix 1: ECOG Performance Status Scale

These scales and criteria are used by doctors and researchers to assess how a patient's disease is progressing, assess how the disease affects the daily living abilities of the patient, and determine appropriate treatment and prognosis.

ECOG PERFORMANCE STATUS*

Grade	ECOG
0	Fully active, able to carry on all pre-disease performance without restriction
1	Restricted in physically strenuous activity but ambulatory and able to carry out work of a light or sedentary nature, e.g., light house work, office work
2	Ambulatory and capable of all self-care but unable to carry out any work activities. Up and about more than 50% of waking hours
3	Capable of only limited self-care, confined to bed or chair more than 50% of waking hours
4	Completely disabled. Cannot carry out any self-care. Totally confined to bed or chair
5	Dead

ECOG=Eastern Cooperative Oncology Group

* As published in Am. J. Clin. Oncol.: Oken, M.M., Creech, R.H., Tormey, D.C., Horton, J., Davis, T.E., McFadden, E.T., Carbone, P.P.: Toxicity And Response Criteria Of The Eastern Cooperative Oncology Group. Am J Clin Oncol 5:649-655, 1982.

17.2 Appendix 2: Highly Effective Methods of Contraception

For countries where 2 highly effective methods of contraception are required, the following definitions are provided (ICH M3).

Highly effective method of contraception / birth control as defined in ICH (M3)

Methods of birth control which result in a low failure rate (i.e., less than 1% per year) when used consistently and correctly such as implants, injectables, combined oral contraceptives, some intrauterine devices (IUDs), sexual abstinence or vasectomized partner.

Barrier Contraceptive

A contraceptive device that physically prevents sperm from entering the endometrial cavity and fallopian tubes (e.g., male condom, female condom or diaphragm).

Acceptable forms of effective contraception include:

- (1) Established use of oral, injected or implanted hormonal methods of contraception. *(Safe hormonal contraceptives include contraceptive pills, implants, transdermal patches, hormonal vaginal devices or injections with prolonged release.) [The decision to allow use of hormonal contraceptives should be based on the Investigational Medicinal Product's metabolism and potential for interactions, pharmacology and the adverse event profile (e.g. vomiting)].*
- (2) Placement of an intrauterine device or intrauterine system. *[Consideration should be given to the type of device or system being used, as there are higher failure rates quoted for certain types, e.g. steel or copper wire]*
- (3) Barrier methods of contraception: Condom or Occlusive cap (diaphragm or cervical/vault caps) with spermicidal foam/gel/film/cream/suppository. *[The use of barrier contraceptives should always be supplemented with the use of a spermicide. The following should be noted:*
 - *Failure rates indicate that, when used alone, the diaphragm and condom are not highly effective forms of contraception. Therefore the use of additional spermicides does confer additional theoretical contraceptive protection.*
 - *However, spermicides alone are inefficient at preventing pregnancy when the whole ejaculate is spilled. **Therefore, spermicides are not a barrier method of contraception and should not be used alone.***
- (4) Male sterilization (with the appropriate post-vasectomy documentation of the absence of sperm in the ejaculate). *[For female subjects on the study, the vasectomized male partner should be the sole partner for that subject].*
- (5) True abstinence: When this is in line with the preferred and usual lifestyle of the subject. *[Periodic abstinence (e.g., calendar, ovulation, symptothermal, post-ovulation methods) and withdrawal are not acceptable methods of contraception].*

Two forms of highly effective contraception

For certain studies, e.g. in the event of teratogenicity or lack of adequate reproductive toxicity data, there is a requirement for 2 forms of highly effective contraception. In this situation, subjects should be instructed to use 2 different forms of effective contraception (e.g. from the list above).

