 - a) Adequate contraception for women is defined as hormonal birth control or an intrauterine device (safe hormonal contraceptives include contraceptive pills, implants, transdermal patches, hormonal vaginal devices or injections with prolonged release). In countries where two highly effective methods of contraception are required this will be an inclusion criterion (refer to [Appendix 2](#)).
 - b) Male patients must be willing to use a latex condom during any sexual contact with females of childbearing potential during and for six months after the last infusion of tisotumab vedotin, even after having undergone a successful vasectomy.
 - c) In order to be considered as sterilized or infertile, a patient must have undergone surgical sterilization (vasectomy/bilateral tubectomy; hysterectomy and bilateral ovariectomy) or be postmenopausal (12 months or more with no period prior to enrolment).

10. Following receipt of verbal and written information about the trial, patients must provide signed informed consent before any trial-related activity is carried out.
11. Acceptable coagulation status as defined in the applicable base protocol:
 - GEN701: Acceptable coagulation status: international normalized ratio (INR) ≤ 1.2 (without anticoagulant therapy) and activated partial thromboplastin time (aPTT) ≤ 1.25 ULN; patients on stable doses of therapeutic anti-coagulative treatment for ≥ 8 weeks (e.g., warfarin) must have an INR ≤ 3 .
 - GEN702: Acceptable coagulation status defined as: INR ≤ 1.2 (without anticoagulant therapy) and aPTT \leq ULN.

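### Criterion 9a requires two highly effective contraceptive methods in some countries, but the Appendix 2 instruction that implements it asks only for two effective ones, from a list that includes barrier methods.

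*Protocol*

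**What the plan says.** Criterion 9a in protocol section 8.5.1 has two parts. The general part reads "Adequate contraception for women is defined as hormonal birth control or an intrauterine device". The country-specific part reads "In countries where two highly effective methods of contraception are required this will be an inclusion criterion", with a reference to Appendix 2. The synopsis repeats both parts without that reference.

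Appendix 2 (section 17.2) opens by giving its purpose: "For countries where 2 highly effective methods of contraception are required, the following definitions are provided (ICH M3". It defines the key term as "Methods of birth control which result in a low failure rate (i.e., less than 1% per year) when used consistently and correctly" and gives examples. These include some intrauterine devices (IUDs), abstinence and a vasectomized partner, but no barrier method. Barrier contraceptives get a separate definition.

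A numbered list of five items follows, under the heading "Acceptable forms of effective contraception include". Item (3) is "Barrier methods of contraception: Condom or Occlusive cap (diaphragm or cervical/vault caps) with spermicidal foam/gel/film/cream/suppository". A note to that item says that "when used alone, the diaphragm and condom are not highly effective forms of contraception", and that added spermicide gives extra protection in theory. Item (2), intrauterine devices, carries a caution that higher failure rates are quoted for certain types.

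The closing paragraph is headed as concerning two highly effective forms and states that requirement. It then says "subjects should be instructed to use 2 different forms of effective contraception (e.g. from the list above".

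**The concern.** The requirement and the instruction that carries it out use different terms, and the instruction uses the weaker one. A site that follows the closing paragraph as written can record criterion 9 as met with a pair of methods that the appendix does not show to be highly effective.

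This is an entry criterion with a safety purpose. The drug carries a microtubule-disrupting agent (section 6). Contraception must continue for six months after the last infusion, and the appendix itself links the two-method rule to teratogenicity or inadequate reproductive toxicity data. Table 1 schedules pregnancy tests at screening and at each cycle start, but none at the End-of-Trial Visit. In the months after treatment, the contraception rule is therefore the only planned safeguard. Section 8.5 permits no waivers of entry criteria, so sites need one unambiguous reading.

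**Working it through.** No sample size, power or event figure is involved. The check sets the texts side by side.

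**Step 1: the standard.** Criterion 9a and the heading of the closing paragraph both say highly effective. The appendix gives that term a meaning: under 1% failure per year with consistent and correct use.

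**Step 2: the instruction.** The sentence that tells subjects what to do says effective and points to the list. The list's heading also says effective. Neither limits the choice to methods that meet the definition, and the sentence offers the list only as an example.

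**Step 3: the five list items against the definition.**

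| Item | Status under the appendix's definition |
|---|---|
| (1) Hormonal | Implants, injectables and combined pills are named as examples |
| (2) Intrauterine device or system | Only some devices are named; item cautions about certain types |
| (3) Barrier with spermicide | Not named; condom and diaphragm alone are said to fall short; no statement that spermicide closes the gap |
| (4) Male sterilization | Named, as vasectomized partner |
| (5) True abstinence | Named |

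The examples are illustrative, so absence from them does not by itself exclude barriers. What matters is the express statement about barriers used alone, together with the lack of any statement that the spermicide combination meets the limit.

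**Step 4: which pairs pass the instruction.** Take different forms to mean different list items. Five items give 5 × 4 / 2 = 10 formal pairs, and 4 of them contain item (3). This counts the wording only; some pairs would not occur in practice.

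- If 9a's general definition still applies, each pair must contain item (1) or (2). That removes the 3 pairs formed from items (3), (4) and (5), leaving 10 − 3 = 7. Two of the 7 contain a barrier: hormonal plus barrier, and IUD plus barrier.
- If Appendix 2 replaces that definition, all 10 pairs are open, and 4 contain a barrier.

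Hormonal plus barrier passes on both readings, with at most one of its two methods shown to be highly effective. IUD plus barrier also passes on both. If the device is of a type the appendix cautions about, neither method is shown to meet the limit. The caution gives no rate, so it does not show that the limit is exceeded either.

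**Step 5: loss of protection.** The documents give no failure rate for barrier plus spermicide or for any pair of methods, so the loss cannot be calculated.

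**The case against.** The best defence is that 9a's general definition has no country limit, that the two-method sentence reads naturally as an addition to it, and that section 8.5.1 requires all criteria to be met. On that reading every woman subject to the criterion has a hormonal method or an IUD, and only the second method can fall short. It can also be said that the appendix's remark on barriers applies to their use alone, while item (3) pairs them with spermicide. Pregnancy tests at each cycle start, and stopping treatment on pregnancy, limit exposure during treatment.

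These points narrow the problem but do not remove it. Even on the additive reading, the second method need not meet the standard that 9a names, and nothing in the appendix says that spermicide brings a barrier up to it.

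The defence does dispose of two stronger readings:

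- A reader might infer that a woman using only a condom and a diaphragm could be enrolled, so that neither of her two methods is highly effective. That requires Appendix 2 to replace 9a's definition. It also requires condom and diaphragm, which share item (3), to count as two forms. The text settles neither.
- A reader might also infer that abstinence or a vasectomized partner makes the same woman ineligible in a one-method country and compliant in a two-method country. That again assumes replacement, and she would still need two methods. Those options appear in Appendix 2 and not in 9a, but a narrow general list beside a country-specific annex is a difference between lists, not necessarily a contradiction.

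**Conclusion.** The inconsistency is real and lies in the wording itself: the requirement says highly effective, its implementing sentence says effective, and no other section resolves this. The firm finding is that a pair such as hormonal plus barrier satisfies the instruction without being shown to satisfy the criterion. This does not depend on how 9a and Appendix 2 relate. Whether a pair with neither a hormonal method nor an IUD could qualify does depend on that, and the protocol is silent.

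The practical reach is unknown. The protocol expects about 25 patients in all, gives no count of women of reproductive potential, and names no country that requires two methods. No endpoint or planned analysis changes; the SAP only lists entry criteria not met. The point merits correction because it concerns an entry and safety rule that sites could apply differently.

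**What to change.** Reconcile the synopsis, criterion 9a and Appendix 2 so that the requirement and its implementing instruction use the same term and the same list. State explicitly:

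- whether a barrier with spermicide counts toward the two methods;
- whether different forms means different list items;
- whether the two-method rule adds to or replaces 9a's general definition for women.

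Which methods are acceptable is for the sponsor to decide; the request is only that the texts agree. The cost is a wording change in three places and matching consent text. Depending on the sponsor's choice, some women may need to change method.
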